3.3 Secondary Study Endpoints

Parent stress and parent and child quality of life will be the secondary study endpoints and be completed by parents at Clinic Visits at weeks 0, 10, 14, and 24.

1. Parent Stress (The Pediatric Inventory for Parents – PIP36). Parent stress will be measured via the Pediatric Inventory for Parents, a 52 item parent questionnaire developed to measure parent stress around caring for a medically complicated child. The measure has a total and four domain scale scores (communication, medical care, role function, emotional function). For the purposes of the current study, we will use only the total score. The measure has been shown to be a valid and reliable measure of pediatric illness-related parenting stress (36).
2. Child Health-Related Quality of Life (Infant Toddler Quality of Life – ITQOL47). Child quality of life in children <5 years old will be measured with the Infant Toddler Quality of Life short form questionnaire, validated for children 2 months through 5 years of age. The ITQOL has 47 items which result in 9 multi-item scales with well-established reliability (Cronbach's alpha > .70) and validity. Similar to our previous work (11), we will use the multi-item scales in our analyses.
3. Child Health-Related Quality of Life (Child Health Questionnaire Parent Form – CHQ-PF50). Child quality of life in children \geq 5 years old will be measured with Child Health Questionnaire Parent Form questionnaire. The parent-reported CHQ is normed for ages 5-to-18 and measures 14 unique physical and psychosocial concepts. The CHQ has 50 items and scores for the parent-reported versions can be analyzed at the concept level (CHQ Profile Scores) or combined to derive an overall physical and psychosocial score, (CHQ Summary Scores).
4. Parent Quality of Life (SF-36v2). Parent Quality of Life will be measured with the widely used Parent Quality of Life Short Form 36, version 2. Over 4000 studies have used the SF-36, making it a widely accepted measure, and v2 has improved reliability ($\alpha = .73-.90$), and validity (38). The 36 questions with 5 point scales have 8 scaled scores: vitality, physical functioning, bodily pain, general health perceptions, physical role functioning, emotional role functioning, social role

CONFIDENTIAL

This material is strictly confidential and is intended solely for the guidance of clinical investigation. Do not disclose or use except as authorized in writing by the study sponsor

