8. Impact of Event Scale – Revised (IES-R). The IES-R is a 22-item self-report measure (for DSM-IV) that assesses subjective distress caused by traumatic events. It is a revised version of the older version, the 15-item IES (Horowitz, Wilner, & Alvarez, 1979). The IES-R contains seven additional items related to the hyperarousal symptoms of PTSD, which were not included in the original IES. Items correspond directly to 14 of the 17 DSM-IV symptoms of PTSD. Respondents are asked to identify a specific stressful life event and then indicate how much they were distressed or bothered during the past seven days by each "difficulty" listed.
9. Demographics. Families will complete a demographic questionnaire regarding age, race, ethnicity, income, free/reduced lunch status, and parental education, along with a medical history questionnaire asking about diagnoses at birth and diagnoses at week 0. These variables will be used to describe our sample and in any covariate analyses
10. Gut microbiota. Stool will be collected at each of the 4 clinic visits (Weeks 0, 10, 14 and 24). Once participants are consented, they will be provided with a toilet hat and sterile cup for stool collection. Once collected, stool will be stored in the sterile collection cup in the participant's freezer, until it is transferred or shipped on ice to a -80° C freezer at the study site. Each sample will be labeled with less than 8 characters and each label which matches the participant ID and will start with a letter (labels may not start with a number; per Novogene guidelines). Micro tubes will be shipped on dry ice to Novogene, where samples will undergo 16s rDNA sequencing utilizing HiSeq PE250. Sequencing will occur in the V4 region with primer 515F and 806R. Data output will be 100,000 raw reads per sample.
11. Clinical care measures. Height, weight, and vital signs will be obtained at clinic visits 1-4. These measures are routine clinical care, but will the data will be used for research purposes.

CONFIDENTIAL

This material is strictly confidential and is intended solely for the guidance of clinical investigation. Do not disclose or use except as authorized in writing by the study sponsor

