5.1 Description

Megestrol

Megestrol is a steroid and progestational drug FDA approved for treating anorexia or weight loss in patients with acquired immunodeficiency syndrome. Its use in the current protocol is “off label” to stimulate appetite in tube-fed infants and toddlers who are weaning from tube feedings and learning to eat. The precise mechanism of action that leads to increased appetite and weight gain is unknown, but is probably related to megestrol’s glucocorticoid effect (41). Side effects of megestrol include suppression of the adrenal glands and new onset diabetes mellitus (41). These complications are minimized by limiting the duration of treatment to 6 weeks (41). Other side effects include heart failure, nausea and vomiting, edema, dyspnea, hyperglycemia, alopecia, hypertension, carpal tunnel syndrome, mood changes, malaise, asthenia, lethargy, sweating and rash (41). Megestrol’s safety and effectiveness have not been established in children. However, there are several pediatric trials with megestrol for anorexia or malnutrition (42-44). In a megestrol trial for children with cystic fibrosis, the youngest child treated was 6 months of age and treated with 10 mg megestrol/day (42). The proposed study will use megestrol 6 mg/kg/day in two doses because this dose has been effective and safe in two previous studies using megestrol to stimulate appetite in children transitioning from tube to oral feedings. (6,45). Megestrol will be dosed at 6 mg/kg/d at weeks 10-11, at 4 mg/kg/d at week 12, at 2 mg/kg/d at week 13, and fully tapered at the end of week 13. Megestrol is absorbed from the small bowel, so feeding it through the tube will be acceptable (41).

Placebo Group

Subjects randomized to the placebo protocol will receive a placebo syrup identical in taste and smell to megestrol at the same intervals as those in the megestrol group but the syrup will contain no active ingredients.

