7.1 Sample Size Determination and Statistical Methods

For Aim1 (To assess the efficacy of megestrol as part of the 24 week iKanEat protocol), if at least 90% of the treatment group successfully transitions (in pilot 100% successfully transitioned), with 72 participants, we would have .80 power to detect an odds ratio of .21. With 60 participants, we would have power to detect an odds ratio of .18. If only 75% of the treatment group successfully transitions, we will still have .80 power to detect an odds ratio of .25 with our smallest expected sample size of 60.

For Aim 2 (To assess the safety of megestrol as part of the 24 week iKanEat protocol), all analyses are descriptive, so a power analysis is not conducted.

For Aim 3 (To examine the effect of the transition from tube to oral feeding on parent stress and parent and child quality of life), with 60 participants, we would have .78 power to detect differences in slopes over the four data points equivalent to a standardized effect size of $d=.75$ or larger. With a sample size of 72, there will be .80 power to detect a difference in slopes equivalent to a standardized effect size of .70. To answer those questions in which the grouping factor is success in treatment, such as 3A (The transition to oral feeding will temporarily increase parent stress at week 14 at the cessation of tube feeding, with a return to baseline by week 24) and 3B (The transition to oral feeding will increase parent/child quality of life at 24 weeks compared to week 0), assuming that 60% of the participants across groups are successful, we would have sufficient power to detect effects equivalent to a standardized effect size of $d=.42$ or larger. With a sample size of 60, the minimum detectable effect size would increase to $d=.59$. If 70% percent are successful, with 72 participants we can detect effects equivalent to $d=.61$, and with 60 participants $d=.70$. These are moderate sized effects.

Planned Analyses

CONFIDENTIAL

This material is strictly confidential and is intended solely for the guidance of clinical investigation. Do not disclose or use except as authorized in writing by the study sponsor

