To address Aim 3, we will model parent stress levels, child quality of life, and parent quality of life for participants in both treatment conditions over the four measurement occasions using General Linear Mixed Models. As in Aim 1, fixed effects for site will be added to the model as will sex and age at initiation. Once the shape of the trajectory over time has been modeled, a successful transition to oral feeding indicator, defined as consuming 90% or more of calories orally, will be added to the model at level 2. For 3A, the primary variable of interest will be the time by successful transition interaction on parental stress level. Estimate statements will examine group differences in stress at week 14 and 24. To address hypothesis 3B regarding Quality of Life outcomes, we will initially model the trajectory over time for each outcome with the same set of predictors as in 3A. Of primary interest will be the time by successful transition interaction on subscales for parental quality of life and the parent impact time, general health perceptions, growth and development, and parent impact emotional subscales for child quality of life which showed the greatest response to intervention in our pilot data. It is expected that some subscales such as general health perceptions and parent impact time will show more response to intervention than others. A significant positive slope for some quality of life indicators are hypothesized for those children who transition to oral feeding while stable or declining quality of life ratings are expected for those who are unable to transition to oral feeding. Finally, to complete our analyses of sex as a biological variable (SABV) we will assess study outcomes by gender.

To address Aim 4, the Shannon Index⁶⁰ will be used to determine microbial diversity. Data analysis will be completed using the paired t-test unless the data is not normally distributed in which case analysis will be completed with the Wilcoxon Signed Rank test to compare the index values of patients on each diet.

Heterogeneity of Subjects

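### The Aim 3 models list no term for randomized arm, so no arm comparison is written for parent stress or quality of life, and the success contrast could absorb part of any direct drug effect

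*Combined protocol and SAP*

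**What the plan says.** Section 3.3 states: "Parent stress and parent and child quality of life will be the secondary study endpoints". Section 7.1 (Planned Analyses, Aim 3) models these outcomes "for participants in both treatment conditions over the four measurement occasions using General Linear Mixed Models". The covariates are given as: "As in Aim 1, fixed effects for site will be added to the model as will sex and age at initiation". Once the time course has been fitted, "a successful transition to oral feeding indicator, defined as consuming 90% or more of calories orally, will be added to the model at level 2", and the effect of interest is its interaction with time. Hypothesis 3B reuses the 3A predictors. Estimate statements then contrast groups on stress at weeks 14 and 24, without saying which groups.

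The Aim 1 model, by contrast, lists treatment condition and its interactions. Aim 2 uses arm descriptively for abnormal cortisol. Aim 4 compares diets.

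The power text in section 7.1 says of Aim 3 that with 60 participants "we would have .78 power to detect differences in slopes over the four data points" at d = .75, and gives .80 at d = .70 with 72. It then deals separately with questions grouped by treatment success.

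Section 3.3 (item 11) adds: "Height, weight, and vital signs will be obtained at clinic visits 1-4". It continues: "These measures are routine clinical care, but will the data will be used for research purposes". No analysis of weight or height appears under Planned Analyses.

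**The concern.** Two things are at stake.

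First, the trial is meant to show whether megestrol's benefit within the feeding program outweighs its risk. The randomized comparison of stress and quality of life bears directly on that question. The data are collected, but no written model estimates the difference.

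Second, the contrast that is written compares children by a post-randomization outcome. Hypothesis 1 expects arm to drive that outcome. Section 5.1 lists side effects including "mood changes, malaise, asthenia, lethargy, sweating and rash", and section 1.2 links the drug to appetite and weight gain. Section 1.3 describes the weight loss of weeks 10-14 as a stressful period in which some parents withdrew their children. Megestrol could therefore move scores by a route other than reaching 90% oral calories. With arm left out, some of that would appear as an effect of transition.

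**Working it through.** **1. Which terms are in which model (section 7.1)**

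| Analysis | Predictors listed | Arm listed? |
|---|---|---|
| Aim 1 | site, sex, age, treatment condition and its interactions | yes |
| Aim 3A | time, site, sex, age, success, time × success | no |
| Aim 3B | same as 3A | no |
| Aim 4 | diet | no |

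Saying that children from both arms are modelled describes the sample. It is not a model term.

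**2. The plan's own slope power**

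The documents give no alpha for this, so I assume two-sided 0.05. With a fraction f in one group, the normal approximation is power = Φ(d√(N f(1−f)) − 1.96).

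- N=60, d=.75, f=.5: Φ(2.905 − 1.96) = .828. The t-test value is .815; stated .78.
- N=72, d=.70, f=.5: Φ(2.970 − 1.96) = .844. The t-test value is .834; stated .80.

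| Split | N=60, d=.75 (t) | N=72, d=.70 (t) | Ratio |
|---|---|---|---|
| 50/50 | .815 | .834 | .977 |
| 60/40 | .799 | .819 | .976 |
| 65/35 | .778 | .798 | .975 |
| Stated | .78 | .80 | .975 |

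The ratio hardly moves with the split. The levels fit an uneven split better than 1:1 arms, although an unstated variance inflation of about 1.12 to 1.13 under 1:1 would also give them. The numbers do not identify the grouping. Only the order of the text, with success-grouped questions taken up separately afterwards, points to arm.

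**3. Share of a direct arm effect absorbed by success when arm is omitted**

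The placebo rates follow from the Aim 1 odds ratios at N=60.

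- Scenario A: 90% on megestrol, OR .18. Placebo odds = 9 × .18 = 1.62, so the rate is 1.62/2.62 = 61.8%.
- Scenario B: 75% on megestrol, OR .25. Placebo odds = 3 × .25 = .75, so the rate is .75/1.75 = 42.9%.

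With 1:1 allocation, share = P(megestrol | success) − P(megestrol | failure).

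- A: .9/(.9+.618) − .1/(.1+.382) = .593 − .208 = .385.
- B: .75/(.75+.429) − .25/(.25+.571) = .636 − .304 = .332.
- Equal rates: 0.

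The documents give no direct effect size, so D is an assumption and a range is shown. The simulation used N=60, one time point, residual SD 1, no true transition effect and 4,000 runs.

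| D (SD) | A: formula / simulated / rejection | B: formula / simulated / rejection |
|---|---|---|
| 0.25 | 0.10 / 0.10 / 6.2% | 0.08 / 0.08 / 5.2% |
| 0.50 | 0.19 / 0.19 / 9.6% | 0.17 / 0.17 / 9.8% |
| 0.75 | 0.29 / 0.29 / 15.0% | 0.25 / 0.26 / 15.6% |

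With arm in the model, simulated bias was at most 0.01 SD and rejection about 5%. At 75% in both arms, bias was about 0 even without arm.

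**4. Price of adding arm (N=60, 80% power)**

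Minimum detectable effect (MDE) for transition = 2.8016/√(N T(1−T)), where T is overall success. Adding arm multiplies it by √[1/(1−φ²)], with φ² = (p1−p2)²/[4T(1−T)].

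- A: T=.759, φ²=.108, variance inflation 1.12. The MDE goes from 0.846 to 0.896.
- B: T=.589, φ²=.107, variance inflation 1.12. The MDE goes from 0.735 to 0.778.

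For the arm comparison itself, a t-test has an MDE of 0.74 at N=60 and 0.67 at N=72.

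The plan's stated detectable effects for success-grouped questions (.42, .59, .61, .70) come out at .68, .75, .73 and .80 with a two-sided t-test at 80% power, so I do not use them as a benchmark.

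**The case against.** Aim 3 asks about the effect of transition, so a model built around success answers its stated question. Arm is already used for the primary outcome and, descriptively, for cortisol. That stands: the arm comparison is an additional secondary analysis, not a correction of what Aim 3 set out to ask.

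Four stronger readings are tempting, and the documents do not support them.

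- *The .78/.80 power can only refer to the arms.* A 65/35 split reproduces both figures, and that lies between the plan's 60% and 70% success assumptions.
- *The plan decided to exclude arm.* The word *group* in the week 14 and 24 contrasts is undefined. In sequence it reads as the transition group, but arm is not ruled out. The power and analysis texts are unreconciled, which is weaker than a deliberate exclusion.
- *Part of megestrol's effect is credited to transition.* This requires both a difference in transition rates and a separate route to the scores. An effect acting through transition is properly a transition effect. The side effects in section 5.1 concern the treated patient rather than parent stress. Dosing ends with week 13, about ten weeks before the week 24 contrast.
- *The weight effect is misattributed too.* Weight is not an Aim 3 outcome. It is a research measure without a written analysis.

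It is also fair to say that the rates used above are detectable alternatives, not forecasts. Scenario B, with 59% overall success, is closer to the plan's Aim 3 assumptions than scenario A, with 76%. Adjusting for arm also leaves other prognostic differences between successes and failures untouched.

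**Conclusion.** The point holds as an omission and an inconsistency. As written, the named secondary endpoints get no explicit randomized comparison, and the slope-difference power has no clearly matching analysis. If megestrol changes the transition rate and also affects scores directly, the success contrast absorbs roughly one third of the direct effect (0.33 to 0.39). That is 0.08 to 0.10, 0.17 to 0.19 or 0.26 to 0.29 SD (simulated) for assumed direct effects of 0.25, 0.5 or 0.75 SD. If either condition fails, it absorbs nothing. These figures rest on the success rates implied by the Aim 1 power text, 1:1 allocation and a single-time-point simplification of the mixed model. The gap should be repaired, but it does not bear on the primary analysis.

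**What to change.** In section 7.1, Aim 3:

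1. Add randomized arm and arm-by-visit to the models.
2. Report the megestrol-placebo difference in change from week 0 to weeks 14 and 24 for the PIP and the quality-of-life scales, in the all-randomized population the plan already defines. Label it secondary, without a confirmatory claim.
3. Keep arm and arm-by-visit in the model when the success indicator is added, and describe the success contrast as non-randomized.
4. Define *group* in the estimate statements, and state the grouping and alpha behind each Aim 3 power figure.
5. Optionally, add an exploratory by-arm summary of the weight already collected.

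This costs wording only: no new patients and no new measurements. The statistical price at N=60 is a rise in the transition MDE from about 0.85 to 0.90 or from 0.74 to 0.78, plus further contrasts without multiplicity adjustment. One limit should be stated in the text. The minimum follow-up for withdrawn children in section 4.4.2 covers height, weight and diet recall but not the questionnaires, so the all-randomized comparison will rest on a missing-data assumption for those families.

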Aim 3: To examine the effect of the transition from tube to oral feeding on parent stress and parent and child quality of life. Hypothesis 3A: The transition to oral feeding will temporarily increase parent stress at week 14 at the cessation of tube feeding, with a return to baseline by week 24. Hypothesis 3B: The transition to oral feeding will increase parent/child quality of life at 24 weeks compared to week 0. Children with feeding tubes have few options for treatment other than extensive inpatient stays and expensive day treatment programs. iKanEat offers an outpatient, less intensive, empirically supported effective treatment option that can improve the lives of children and families. It is imperative that we determine the efficacy and safety of the protocol including 4 weeks of megestrol before we move toward broad dissemination of the iKanEat protocol.

Aim 4: To examine the effect of the transition from tube to oral feeding on the gut microbiome. Hypothesis 4A: The transition to oral feeding will increase the variety of food consumed orally, thus diversifying the gut microbiome by week 24. Hypothesis 4B: Children who are on a blended diet formula at week 0 will have a more diverse microbiome than children on commercially prepared formula prior to transitioning to oral feeding (Week 0, 10). Little is known about the gut microbiota of children who transition from formula feeding to oral feeding. Determining the changes in the gut microbiome could add to general knowledge about how the gut microbiome adapts to changes in diet over time in children who transition from commercial or blended formulas to a diet consumed orally.

CONFIDENTIAL

This material is strictly confidential and is intended solely for the guidance of clinical investigation. Do not disclose or use except as authorized in writing by the study sponsor

3 Study Design

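### Hypothesis 3A predicts a rise in parent stress at week 14 only, but the plan reads it off a trajectory shape that is still to be chosen, and some shapes would remove half or more of it

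*Combined protocol and SAP*

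**What the plan says.** Section 2 (Study Aims, Aim 3) predicts that weaning from the tube "will temporarily increase parent stress at week 14 at the cessation of tube feeding, with a return to baseline by week 24". It makes no prediction for week 10. Under section 3.3 the stress and quality-of-life measures are to "be completed by parents at Clinic Visits at weeks 0, 10, 14, and 24", so there are four time points.

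The Planned Analyses for Aim 3 (section 7.1) model the outcomes "over the four measurement occasions using General Linear Mixed Models". The order of model building is explicit: "Once the shape of the trajectory over time has been modeled, a successful transition to oral feeding indicator" is added at level 2. For 3A, "the primary variable of interest will be the time by successful transition interaction on parental stress level", and "Estimate statements will examine group differences in stress at week 14 and 24". I read the groups in that last sentence as successful and unsuccessful children. The plan does not say whether time is categorical or continuous, which shapes are candidates, how one is chosen, or which covariance structure is used.

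The sample-size text in section 7.1 gives two sets of Aim 3 figures. The first concerns slopes: with 60 participants, "we would have .78 power to detect differences in slopes over the four data points" at d=.75, and .80 at d=.70 with 72. The second is for questions grouped by treatment success, and it names 3A and 3B. With 60% successful the detectable d is .42 (read as N=72) or .59 (N=60). With 70% successful it is .61 (N=72) or .70 (N=60). These are described as effects, with no contrast named.

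**The concern.** A departure at one of four visits is not a slope, and a smooth low-order curve cannot follow it. The contrasts at weeks 14 and 24 target the right visits, but they inherit whatever time coding was settled on before the success indicator entered. If that coding is linear or quadratic, part of a real week 14 rise is spread over the other visits.

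The shape is also chosen while successful and unsuccessful children are pooled. A rise confined to successful children is diluted at exactly that step, which makes a shape that is too simple more likely. The period matters to the sponsor: section 1.3 (Parent Stress) reports that parents in the previous trial withdrew children during the expected weight loss around the wean, and it gives this as the reason to study stress over time.

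**Working it through.** **1. The plan's own power figures.** A two-sided .05 t-test with equal groups gives 0.815 at d=.75, N=60 (stated .78) and 0.834 at d=.70, N=72 (stated .80). A 65:35 split gives 0.778 and 0.798. Alpha, sidedness, split, correlation and slope variance are not stated, so I do not call these figures wrong. They concern slopes, and the steps below do not use them.

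**2. What each shape keeps.** Inputs: weeks 0, 10, 14, 24 (section 3.3) and a true group difference of (0, 0, 1, 0), in units of the week 14 rise. The zero at week 10 is my assumption. The fits are least squares with complete data; compound symmetry gives the same values.

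- *Linear.* Mean time is 12, the deviations are (−12, −2, 2, 12), and their sum of squares is 296. Slope = 2/296 = 0.00676; mean difference = 0.25. Week 14: 0.25 + 2 × 0.00676 = 0.264. Week 24: 0.25 + 12 × 0.00676 = 0.331. Week 0: 0.25 − 0.081 = 0.169.
- *Quadratic.* The only direction lost is the cubic contrast c = (−1, 6, −6, 1), with squared length 74. Here c·y = −6, so the fit is y + (6/74)c = (−0.081, 0.486, 0.514, 0.081).
- *Cubic or four-level time.* Saturated with four visits, so the fit is exact: 1.00 at week 14 and 0 elsewhere.

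| Time coding | Week 10 | Week 14 | Week 24 | Week 14 minus week 0 |
|---|---|---|---|---|
| Linear | 0.236 | 0.264 | 0.331 | 0.095 |
| Quadratic | 0.486 | 0.514 | 0.081 | 0.595 |
| Cubic / categorical | 0 | 1.00 | 0 | 1.00 |

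Under the autoregressive covariances tried (parameter .3 to .9), the linear week 14 value falls to between 0.18 and 0.03, and the quadratic stays near 0.50.

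**3. Sensitivity to week 10.** For a profile (0, 0.5, 1, 0), c·y = 3 − 6 = −3, and the quadratic week 14 value is 1 − 18/74 = 0.757.

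**4. Power for the week 14 minus week 0 group contrast.** Inputs from section 7.1: N=60, 60% successful (36 and 24), d=.59. Assumed: two-sided .05, SD 1, compound symmetry with correlation ρ = .5 or .7. Write g = 1/36 + 1/24 = 0.0694.

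- *Categorical:* SE = √(2(1−ρ)g) = 0.264 or 0.204; z = 2.24 or 2.89; power Φ(z − 1.96) = 0.61 or 0.82.
- *Quadratic:* effect 0.595 × .59 = 0.351; SE = √((2 − 25/74)(1−ρ)g) = 0.240 or 0.186; power 0.31 or 0.47.
- *Linear time-by-success slope:* effect .59 × 2/296 = 0.0040; SE = √((1−ρ)g/296) = 0.0108 or 0.0084; power 0.06 or 0.07.

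**5. Choosing the shape from the pooled curve.** In the same setting the pooled rise is .6 × .59 = .354 SD. With ρ = .5, the pooled linear, quadratic and cubic terms have expected z of 0.45, 1.94 and 2.70, so they reach p < .05 with probability about .07, .49 and .77. Selection was simulated over the plan's four combinations of N, success share and d, with ρ of .5 to .7. Building up from linear keeps on average 0.42 to 0.93 of the week 14 difference. Testing down from cubic keeps 0.67 to about 1.0.

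**6. Type I error of the interaction test.** With n1 and n2 children per group and common covariance V, Cov(pooled mean, group difference) = (n1/N)(V/n1) − (n2/N)(V/n2) = 0. With complete data, selection on pooled time terms is therefore independent of the group contrasts under normality. Simulation under no group difference (20,000 trials per case, ρ = .5) rejected in 4.9% to 5.2%.

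**The case against.** The plan names neither a linear nor a quadratic curve. A competent analyst could pick cubic or categorical time, lose nothing, and read the planned week 14 and 24 contrasts correctly. Testing down from cubic also does well at the larger effect sizes. All of this stands, so the loss is conditional. It does not remove the point, because the plan does describe a procedure (shape first on pooled data, success afterwards), and the contrasts are only as good as the shape it yields.

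Three stronger readings are tempting, and the documents do not support them:

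- *That the plan necessarily flattens the rise to between a quarter and a half.* This holds only for a linear or quadratic choice and a week 14-only departure. Week 10 stress could already be raised: families receive study drug at that visit, and the tube taper starts five days later (section 6.4).
- *That Aim 3 is sized only on slopes.* Section 7.1 gives separate detectable effects for 3A and 3B. The remaining gap is that no contrast is named for them.
- *That choosing the shape on the same data leaves the error rate unknown.* For the time-by-success test, step 6 shows the error stays near 5% under its assumptions. Selection costs power and accuracy at week 14; inflated error was not shown.

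Parent stress is a secondary endpoint, and Aim 1 is unaffected.

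**Conclusion.** The concern holds in conditional form. The Aim 3 analysis leaves the coding of time to an unspecified search on pooled data, and 3A is the hypothesis most sensitive to that choice. For a departure at week 14 only, the retained share is 0.26 (linear), 0.51 (quadratic) or 1.00 (cubic or categorical). Under data-driven selection it averages roughly 0.4 to 1.0. At the plan's d=.59 with 60 children, power for change from week 0 to week 14 is 0.61 to 0.82 with categorical time, against 0.31 to 0.47 with quadratic time.

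The retained shares for fixed shapes rest on the assumed profile and on complete data with independent or compound-symmetric errors. The power and selection figures also rest on assumed correlations of .5 to .7 and two-sided .05 tests. The change is worth making: the remedy is better than the stated procedure and uses data already scheduled.

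**What to change.** For 3A only:

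1. Replace the shape-finding step with time as a four-level factor (weeks 0, 10, 14, 24) and its interaction with the success indicator. Keep the planned site, sex and age terms.
2. Prespecify the group contrasts at week 14 and week 24, both as levels and as change from week 0.
3. Name the covariance structure, with a fallback if an unstructured matrix does not converge.
4. In section 7.1, say which contrast the 3A detectable effects (d=.42 to .70) refer to, and restate them for the week 14 contrast with alpha, sidedness and within-person correlation given. This would also clear up their scaling. Moving from 72 to 60 participants should raise d by about √(72/60) = 1.10, but .59/.42 = 1.40 and .70/.61 = 1.15.

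The 3B hypothesis is worded partly in terms of slopes and can keep its own model.

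Cost: a wording change and no new data. The model has two more time terms and two more interaction terms than a linear one. An unstructured covariance has 4 × 5/2 = 10 parameters, alongside the site indicators, which is a real but manageable load with 60 children.
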